8.1.2.3 DIRECTED PHYSICAL EXAM

For cycles that do not require a full physical exam per the Schedule of Events, the investigator or qualified designee will perform a directed physical exam as clinically indicated prior to trial treatment administration.

8.1.2.4 VITAL SIGNS

The investigator or qualified designee will take vital signs at screening, prior to the administration of each dose of trial treatment, at treatment discontinuation and follow-up as specified in the Schedule of Events (Section 1.3). Vital signs should include temperature, pulse, respiratory rate, weight and blood pressure. Height will be measured at screening only.

8.1.2.5 EASTERN COOPERATIVE ONCOLOGY GROUP (ECOG) PERFORMANCE SCALE

The investigator or qualified designee will assess ECOG status (see Appendix 1) at screening, prior to the administration of each dose of trial treatment, discontinuation of trial treatment, and at 30 day Safety Follow-up as specified in the Schedule of Events.

8.1.2.6 TUMOR IMAGING AND ASSESSMENT OF DISEASE

Tumor imaging is strongly preferred to be acquired by computed tomography (CT). For the abdomen and pelvis, contrast-enhanced magnetic resonance imaging (MRI) may be used when CT with iodinated contrast is contraindicated, or when local practice mandates it. MRI is the strongly preferred modality for imaging the brain. The same imaging technique regarding modality, ideally the same scanner, and the use of contrast should be used in a participant throughout the study to optimize the reproducibility of the assessment of existing and new tumor burden and improve the accuracy of the assessment of response or progression based on imaging.

8.1.2.6.1 INITIAL TUMOR IMAGING

Initial tumor imaging at Screening must be performed within 28 days prior to the date of allocation. The site study team must review screening images to confirm the participant has measurable disease per RECIST 1.1.

Tumor Imaging During the Study

The first on-study imaging assessment should be performed at 9 weeks (63 days \pm 7 days) from the date of allocation. Subsequent tumor imaging should be performed every 9 weeks (63 days \pm 7 days) or more frequently if clinically indicated. Imaging timing should follow calendar days and should not be adjusted for delays in cycle starts. Imaging should continue to be performed until disease progression is identified by the Investigator.

Objective response should be confirmed by a repeat imaging assessment. Tumor imaging to confirm PR or CR should be performed at least 4 weeks after the first indication of a response is observed. Participants will then return to regular scheduled imaging every 9 weeks, starting with the next scheduled imaging time point. Participants who receive additional imaging for confirmation do not need to undergo the next scheduled tumor imaging if it is less than 4 weeks later; tumor imaging may resume at the subsequent scheduled imaging time point.

Per iRECIST (Appendix 4), disease progression should be confirmed by the site 4 to 8 weeks after first radiologic evidence of PD in clinically stable participants. Participants who have unconfirmed disease progression may continue on treatment at the discretion of the Investigator until progression is confirmed by the site provided they have met the conditions detailed in Appendix 4. Participants who receive confirmatory imaging do not need to undergo the next scheduled tumor imaging if it is less than 4 weeks later; tumor imaging may resume at the subsequent scheduled imaging time point, if clinically stable. Participants who have confirmed disease progression by iRECIST, as assessed by the site, will discontinue study treatment, but continued to be followed for survival as per Schedule of Events. **Exceptions are detailed in Appendix 4.**

8.1.2.6.2 END OF TREATMENT AND FOLLOW-UP TUMOR IMAGING

In participants who discontinue study treatment, tumor imaging should be performed at the time of treatment discontinuation (\pm 7 days). If previous imaging was obtained within

8 weeks prior to the date of discontinuation, then imaging at treatment discontinuation is not mandatory. In participants who discontinue study treatment due to documented disease progression and the Investigator elects not to implement iRECIST, this is the final required tumor imaging.

In participants who discontinue study treatment without documented disease progression, every effort should be made to continue monitoring their disease status by tumor imaging every 12 weeks to monitor disease status until the start of a new anticancer treatment, disease progression, pregnancy, death, withdrawal of consent, or the end of the study, whichever occurs first.

8.1.2.6.3 SECOND COURSE (RETREATMENT) TUMOR IMAGING

Tumor imaging must be performed within 14 days prior to restarting treatment with pembrolizumab. Local reading (Investigator assessment with site radiology reading) will be used to determine eligibility.

The first on-study imaging assessment should be performed at 9 weeks (63 days \pm 7 days) after the restart of treatment. Subsequent tumor imaging should be performed every 9 weeks (63 days \pm 7 days) or more frequently, if clinically indicated.

Per RECIST 1.1, if tumor imaging shows initial PD, tumor assessment should be repeated 4 to 8 weeks later in order to confirm PD with the option of continuing treatment while awaiting radiologic confirmation of progression. Participants who obtain confirmatory imaging do not need to undergo scheduled tumor imaging if it is less than 4 weeks later and may wait until the next scheduled imaging time point, if clinically stable.

Imaging should continue to be performed until disease progression, the start of a new anticancer treatment, withdrawal of consent, death, or notification by the Sponsor-Investigator, whichever occurs first. Disease progression may be confirmed 4 to 8 weeks after the first tumor imaging indicating PD, by the Investigator using iRECIST, in clinically stable participants.

In participants who discontinue study treatment, tumor imaging should be performed at the time of treatment discontinuation (\pm 4 week window). If previous imaging was obtained within 4 weeks prior to the date of discontinuation, then imaging at treatment discontinuation is not mandatory. In participants who discontinue study treatment due to documented disease progression, this is the final required tumor imaging.

In participants who discontinue study treatment without documented disease progression, every effort should be made to continue monitoring their disease status by radiologic imaging every 9 weeks (63 days \pm 7 days) until either the start of a new anticancer treatment, disease progression, pregnancy, death, or the end of the study, whichever occurs first.

8.1.2.6.4 RECIST 1.1 ASSESSMENT OF DISEASE

RECIST 1.1 will be used as the primary measure for assessment of tumor response, date of disease progression, and as a basis for all protocol guidelines related to disease status (eg, discontinuation of study treatment). Although RECIST 1.1 references a maximum of 5 target lesions in total and 2 per organ, the Sponsor-Investigator allows a maximum of 10 target lesions in total and 5 per organ, if clinically relevant to enable a broader sampling of tumor burden.

8.1.2.6.5 IRECIST ASSESSMENT OF DISEASE

iRECIST is based on RECIST 1.1, but adapted to account for the unique tumor response seen with immunotherapeutic drugs. When clinically stable, participants should not be discontinued

until progression is confirmed by the Investigator, working with local radiology, according to the rules below. This allowance to continue treatment despite initial radiologic PD takes into account the observation that some participants can have a transient tumor flare in the first few months after the start of immunotherapy, and then experience subsequent disease response.

A description of the adaptations and iRECIST process is provided in Appendix 4, with additional detail in the iRECIST publication [Seymour et al, 2017]. iRECIST will be used by the Investigator to assess tumor response and progression, and make treatment decisions.

Table 2: Imaging and Treatment after First Radiologic Evidence of Progressive Disease

	Clinically Stable		Clinically Unstable	
	Imaging	Treatment	Imaging	Treatment
First radiologic evidence of PD by RECIST 1.1	Repeat imaging at 4 to 8 weeks to confirm PD.	May continue study treatment at the Investigator's discretion while awaiting confirmatory tumor imaging by site by iRECIST.	Repeat imaging at 4 to 8 weeks to confirm PD per Investigator's discretion only.	Discontinue treatment
Repeat tumor imaging confirms PD (iCPD) by iRECIST per Investigator assessment	No additional imaging required.	Discontinue treatment (exception is possible upon consultation with Sponsor-Investigator).	No additional imaging required.	Not applicable
Repeat tumor imaging shows iUPD by iRECIST per Investigator assessment	Repeat imaging at 4 to 8 weeks to confirm PD. May occur at next regularly scheduled imaging visit.	Continue study treatment at the Investigator's discretion.	Repeat imaging at 4 to 8 weeks to confirm PD per Investigator's discretion only.	Discontinue treatment
Repeat tumor imaging shows iSD, iPR, or iCR by iRECIST per Investigator assessment.	Continue regularly scheduled imaging assessments.	Continue study treatment at the Investigator's discretion.	Continue regularly scheduled imaging assessments.	May restart study treatment if condition has improved and/or clinically stable per Investigator's discretion. Next tumor image should occur according to the regular imaging schedule.

iCPD = iRECIST confirmed progressive disease; iCR = iRECIST complete response; iRECIST = modified Response Evaluation Criteria in Solid Tumors 1.1 for immune-based therapeutics; iSD = iRECIST stable disease; iUPD = iRECIST unconfirmed progressive disease; PD = progressive disease; RECIST 1.1 = Response Evaluation Criteria in Solid Tumors 1.1..

8.1.3 LABORATORY PROCEDURES/ASSESSMENTS

Details regarding specific laboratory procedures/assessments to be performed in this trial are provided below.

Laboratory tests for hematology, chemistry, urinalysis, and others are specified in Table 3

Laboratory tests for screening or entry into the Second Course Phase should be performed within 10 days prior to the first dose of treatment. After Cycle 1, pre-dose laboratory procedures can be conducted up to 72 hours prior to dosing. Results must be reviewed by the investigator or qualified designee and found to be acceptable prior to each dose of trial treatment.

Table 3: Laboratory Tests

Hematology	Chemistry	Urinalysis	Other
Hematocrit	Albumin	Blood	Serum β -human chorionic gonadotropin†
Hemoglobin	Alkaline phosphatase	Glucose	(β -hCG)†
Platelet count	Alanine aminotransferase (ALT)	Protein	PT (INR)
WBC (total and differential)	Aspartate aminotransferase (AST)	Specific gravity	aPTT
Red Blood Cell Count	Lactate dehydrogenase (LDH)	Microscopic exam (If abnormal)	Total triiodothyronine (T3)
Absolute Neutrophil Count	Carbon Dioxide ‡	results are noted	Free tyroxine (T4)
Absolute Lymphocyte Count	(CO₂ or biocarbonate)	Urine pregnancy test †	Thyroid stimulating hormone (TSH)
	Uric Acid		PK
	Calcium		
	Chloride		Blood for correlative studies
	Glucose		
	Phosphorus		
	Potassium		
	Sodium		
	Magnesium		
	Total Bilirubin		
	Direct Bilirubin (If total bilirubin is elevated above the upper limit of normal)		
	Total protein		
	Blood Urea Nitrogen		

† Perform on women of childbearing potential only. If urine pregnancy results cannot be confirmed as negative, a serum pregnancy test will be required.

‡ If considered standard of care in your region.

8.1.4 OTHER PROCEDURES

8.1.4.1 WITHDRAWAL/DISCONTINUATION

When a participant discontinues/withdraws prior to trial completion, all applicable activities scheduled for the final trial visit should be performed at the time of discontinuation. Any adverse events which are present at the time of discontinuation/withdrawal should be followed in accordance with the safety requirements outlined in Section 8.4. Participants who a) attain a CR or b) complete 24 months of treatment with pembrolizumab may discontinue treatment with the option of restarting treatment if they meet the criteria specified in Appendix 7. After discontinuing treatment following assessment of CR, these participants should return to the site for a Safety Follow-up Visit (described in Section 8.3) and then proceed to the Follow-Up Period of the study (described in Section 8.3).

8.1.4.2 SCREENING

Screening procedures may be repeated after consultation with the PI.

8.1.4.3 POST-TREATMENT VISITS

Safety Follow-Up Visit

The mandatory Safety Follow-Up Visit should be conducted approximately 30 days after the last dose of study treatment or before the initiation of a new anti-cancer treatment, whichever comes first. If the post-trial visit occurs less than 30 days after the last dose of study treatment, a subsequent follow-up phone call should be made at 30 days post the last dose of study treatment to determine if any adverse events have occurred since the post-trial clinic visit. All AEs that occur prior to the Safety Follow-Up Visit should be recorded. Participants with an AE of Grade > 1 will be followed until the resolution of the AE to Grade 0-1 or until the beginning of a new anti-cancer therapy, whichever occurs first. SAEs that occur within 90 days of the end of treatment or before initiation of a new anti-cancer treatment will also be followed and recorded. Participants who are eligible for retreatment/crossover with pembrolizumab (as described in Appendix 7) may have up to two safety follow-up visits, one after the Initial Treatment Period and one after the Second Course Treatment.

Follow-Up Visits

Participants who discontinue study treatment for a reason other than disease progression will move into the Follow-Up Phase and should be assessed every 12 weeks (42 ± 7 days) by radiologic imaging to monitor disease status. Every effort should be made to collect information regarding disease status until the start of new anti-cancer therapy, disease progression, death, end of the study or if the participant begins retreatment with pembrolizumab as detailed in Appendix 7. Information regarding post-study anti-cancer treatment will be collected if new treatment is initiated.

Participants who are eligible to receive retreatment with pembrolizumab according to the criteria in Appendix 7 will move from the follow-up phase to the Second Course Phase when they experience disease progression.

Survival Follow up

Participants who experience confirmed disease progression or start a new anticancer therapy, will move into the Survival Follow-Up Phase and should be contacted by telephone every 12 weeks to assess for survival status until death, withdrawal of consent, or the end of the trial, whichever occurs first. Patients will be followed for 5 years for survival.

8.2 CORRELATIVE LABORATORY EVALUATION (RESEARCH)

The University of Colorado Pathology Shared Resource, GI Translational Lab/[name] Laboratory, and Human Immune Monitoring Shared Resource (HIMSR) will coordinate and process the sample collection of tissue and blood samples for research related testing at central laboratories. Instruction manuals and supply kits will be provided for all central laboratory assessments.

Exploratory PD-L1 analysis will be conducted by Merck through Qualtek.

Please see lab protocols and forms for instructions.

8.3 ADVERSE EVENTS AND SERIOUS ADVERSE EVENTS

8.3.1 DEFINITION OF ADVERSE EVENTS (AE)

Adverse event means any untoward medical occurrence associated with the use of an intervention in humans, whether or not considered intervention-related (21 CFR 312.32 (a)).

An adverse event can therefore be any unfavorable and unintended sign (including an abnormal laboratory finding, for example), symptom, or disease temporally associated with the use of a medicinal product or protocol-specified procedure, whether or not considered related to the medicinal product or protocol-specified procedure. Any worsening (i.e., any clinically significant

adverse change in frequency and/or intensity) of a preexisting condition that is temporally associated with the use of the Merck's product, is also an adverse event.

Merck product includes any pharmaceutical product, biological product, device, diagnostic agent or protocol-specified procedure, whether investigational (including placebo or active comparator medication) or marketed, manufactured by, licensed by, provided by or distributed by Merck for human use.

Adverse events may occur during the course of the use of Merck product in clinical trials, or as prescribed in clinical practice, from overdose (whether accidental or intentional), from abuse and from withdrawal.

Any medical condition that is present at the time that the participant is screened will be considered as baseline and not reported as an AE.

Changes in the severity of an AE will be documented to allow an assessment of the duration of the event at each level of severity to be performed. AEs, including lab work, characterized as intermittent require documentation of onset and duration of each episode.

All AEs, SAEs and other reportable safety events that occur after the consent form is signed but before treatment must be reported by the investigator if the participant is receiving placebo run-in or other run-in treatment, if the event causes the participant to be excluded from the study, and/or is the result of a protocol-specified intervention, including but not limited to washout or discontinuation of usual therapy, diet, or a procedure.

- All AEs from the time of treatment through 30 days following cessation of study treatment must be collected by the delegated study team. AEs that have an onset greater than 30 days after the last dose of study drug will not be collected.
- All pregnancies and exposure during breastfeeding, from the time of treatment through 120 days following cessation of study treatment, or 30 days following cessation of study treatment if the participant initiates new anticancer therapy must be reported by the investigator.

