1 PROTOCOL SUMMARY

1.1 SYNOPSIS

Protocol Title: A Phase II study of induction SBRT and olaparib followed by combination pembrolizumab/olaparib in gastric and gastroesophageal junction (GEJ) cancers

Objectives:

Primary Objective:

- To assess the anti-tumor efficacy of combined therapy as determined by measurement of objective response rate (ORR)

Secondary Objectives:

- To assess the anti-tumor efficacy of combined therapy as determined by measurement of overall survival (OS), progression free survival (PFS), duration of response (DOR) and disease control rate (DCR) as a total cohort and HRD (Homologous Recombination Deficiency) versus HR (Homologous Recombination) proficient.
- To evaluate the safety and tolerability of radiotherapy added to olaparib.

Tertiary/ Exploratory Objective:

- To define the effect of HRD on combination SBRT (Stereotactic Beam Radiation Therapy), olaparib, and pembrolizumab on immunomodulation as measured by immune cell infiltration and activation in plasma/serum assays and tissue.

Endpoint:

Primary Endpoint:

- Objective Response Rate of unirradiated tumors (ORR per RECIST 1.1)

Secondary Endpoints:

- Overall Survival (OS) from the initiation of therapy to the date of death or to the date of last follow-up.
- Progression Free Survival (PFS) from the initiation of therapy to the date of progression or to the date of last follow-up.
- Duration of response (DoR) defined as the time from documentation of tumor response to disease progression.

- Disease control rate (DCR) defined as the sum of partial response (PR), complete response (CR) and stable disease (SD).
- Treatment-emergent adverse events (AEs), serious adverse events (SAEs) of combination SBRT and olaparib

Tertiary/ exploratory:

- Immune changes in tumor tissue and plasma at baseline compared to after combination SBRT/olaparaib and after Olaparib/pembrolizumab
- Assess response based on HRD status, PD-L1 expression, MMR (Mismatch Repair)/MSI (Microsatellite Instability), and TMB (Tumor Mutational Burden) in tumor
- Changes in cytokines, ctDNA in plasma/serum
- Abscopal effect based on irradiated disease site

Population:

Sample size

- *Maximum number of participants that can be enrolled is 32 (allow for screen failures)*
- *Minimum number of participants to be enrolled 26 (between two cohorts: 13 in the HR deficient cohort, 13 in the HR proficient cohort) (number of participants needed to answer scientific question/aims)*

Phase:

II

Participating Sites:

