^o Drug diaries will be collected and reviewed at the end of each cycle for Olaparib compliance. Additionally, patients should bring any bottles dispensed for the previous cycle with them to each clinic visit (starting at Day 1 cycle 2) for compliance.

^p The simulation planning scan needs to be completed prior to treatment start date. A radiation oncology assessment will occur at least once during the SBRT course as per standard of care. At 2 weeks post-SBRT, a radiation oncology nurse will call patient to assess for any further toxicities. See section 4.3 for additional radiation details.

^q Only Concomitant Medications related to the treatment of AE or SAE, and other medical conditions deemed necessary by the PI will be recorded.

^r For patients who come off treatment for reasons other than progression, follow up scans will be recorded every 12 weeks. Participants who experience confirmed disease progression or start a new anticancer therapy, will move into the Survival Follow-Up Phase and should be contacted by telephone every 12 weeks to assess for survival status until death, withdrawal of consent, or the end of the trial, whichever occurs first. Patients will be followed for 5 years for survival

^s EOT scans are only required if a scan has not been performed within 8 weeks prior to the EOT visit

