2.5 RISK/BENEFIT ASSESSMENT

2.5.1 KNOWN POTENTIAL RISKS

Risks of radiation include the following acute toxicities:

- Generalized fatigue, malaise, anorexia
- Skin changes
- Site specific toxicities include difficulty swallowing, shortness of breath, loss of appetite, nausea/vomiting, bowel cramping, loose stool or diarrhea.
- Late toxicities of GI ulceration or obstruction, esophageal stricture, pneumonitis, renal toxicity, liver toxicity, bone weakening.

Risks of olaparib include the following acute toxicities:

- Generalized effect on energy level
- Hematological toxicity (neutropenia, leukopenia, anemia, thrombocytopenia)
- Gastrointestinal toxicity (nausea, vomiting, diarrhea)
- Pulmonary toxicity (dyspnea, infection)
- Renal toxicity

Risks of pembrolizumab include the following toxicities:

- Pneumonitis
- Diarrhea/Colitis
- AST/ALT elevation or increased bilirubin
- Type 1 diabetes mellitus (T2DM) or Hyperglycemia
- Hypophysitis
- Hyperthyroidism
- Hypothyroidism
- Nephritis and renal dysfunction

- Myocarditis

These immune-related AEs (irAEs) may occur shortly after the first dose or several months after the last dose of pembrolizumab treatment and may affect more than one body system simultaneously.

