8.3.2 DEFINITION OF SERIOUS ADVERSE EVENTS (SAE)

Serious adverse event or serious suspected adverse reaction. An AE or suspected adverse reaction is considered "serious" if, in the view of either the investigator or sponsor, it results in any of the following outcomes: death, a life-threatening adverse event, inpatient hospitalization or prolongation of existing hospitalization, a persistent or significant incapacity or substantial disruption of the ability to conduct normal life functions, or a congenital anomaly/ birth defect. Important medical events that may not result in death, be life-threatening, or require hospitalization

may be considered serious when, based upon appropriate medical judgment, they may jeopardize the patient or subject and may require medical or surgical intervention to prevent one of the outcomes listed in this definition. Examples of such medical events include allergic bronchospasm requiring intensive treatment in an emergency room or at home, blood dyscrasias or convulsions that do not result in inpatient hospitalization, or the development of drug dependency or drug abuse.

Note: In addition to the above criteria, adverse events meeting either of the below criteria, although not serious per ICH definition, are reportable to the Merck in the same timeframe as SAEs to meet certain local requirements. Therefore, these events are considered serious by Merck for collection purposes.

- Is a new cancer (that is not a condition of the study);
- Is associated with an overdose.

All AEs, meeting serious criteria from the time of study treatment through 90 days following cessation of study treatment, or 30 days following cessation of study treatment if the participant initiates new anticancer therapy, whichever is earlier must be collected by the delegated study staff.

Refer to Table in Section 8.4.3.1 for additional details regarding each of the above criteria.

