Additionally, any serious adverse event, considered by an investigator who is a qualified physician to be related to Merck product that is brought to the attention of the investigator at any time following consent through the end of the specified safety follow-up period specified in the paragraph above, or at any time outside of the time period specified in the previous paragraph also must be reported immediately to Merck Global Safety.

All participants with serious adverse events must be followed up for outcome.

A copy of all 15 Day Reports and Annual Progress Reports is submitted as required by FDA, European Union (EU), Pharmaceutical and Medical Devices agency (PMDA) or other local regulators. Investigators will cross reference this submission according to local regulations to the Merck Investigational Compound Number (IND, CSA, etc.) at the time of submission. Additionally investigators will submit a copy of these reports to Merck & Co., Inc. (Attn: Worldwide Product Safety; [contact]) at the time of submission to FDA.

Follow-up of unresolved serious adverse events

Any SAEs that are unresolved at the time of the initial report submission should be followed up by the investigator for as long as medically indicated, and an updated SAE report submitted at the

time new information regarding the event becomes available.

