9.4.5 SAFETY ANALYSES

Safety Assessments

The safety of Olaparib, SBRT and pembrolizumab will be assessed by evaluating study drug exposure, adverse events, serious adverse events, oncology-related events, all deaths, as well as changes in laboratory determinations and vital sign parameters.

Duration of Study Drug

A summarization of the number of days and/or cycles subjects were exposed to study drug will be provided.

Adverse Events

Analyses of adverse events (and serious adverse events) will include only "treatment-emergent" events, i.e., those that have an onset on or after the day of the first dose of study drug. Analyses will not include those that have an onset greater than 30 days after the last dose of study drug. Treatment emergent adverse events will be summarized by system organ class and preferred term according to the MedDRA adverse event coding dictionary. The percentage of subjects experiencing an adverse event at a given severity, NCI CTCAE toxicity grade, and relationship to study drug will be provided.

Deaths

The number of subject deaths will be summarized (1) for deaths occurring while the subject was still receiving study drug in this study, (2) for deaths occurring off treatment within 30 days after the last dose of study drug, and (3) for all deaths in this study regardless of the number of days after the last dose of study drug. The relatedness of the deaths to the study drugs will also be provided.

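### Adverse event follow-up is timed from the last drug dose, so late SBRT toxicity in patients who stop early is only partly collected and, beyond 30 days, not analysed

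*Combined protocol and SAP*

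**What the plan says.** **General AEs.** Section 8.3.1 ends collection 30 days after treatment and adds that "AEs that have an onset greater than 30 days after the last dose of study drug will not be collected".

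**Serious AEs.** Section 8.3.2 requires collection of "All AEs, meeting serious criteria from the time of study treatment through 90 days following cessation of study treatment", cut to 30 days if new anticancer therapy starts; Section 8.3.6 repeats this for reporting. Section 8.1.4.3 words the limit differently: "SAEs that occur within 90 days of the end of treatment or before initiation of a new anti-cancer treatment will also be followed". For SAEs judged related to a Merck product, Section 8.3.6 has no time limit: those coming to light "at any time outside of the time period specified in the previous paragraph also must be reported immediately to Merck Global Safety".

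**Analysis.** Section 9.4.5 limits both AE and SAE summaries to treatment-emergent events and states: "Analyses will not include those that have an onset greater than 30 days after the last dose of study drug". Deaths are the exception and are counted whenever they occur.

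**Radiation.** The Section 6.1.2 table gives SBRT over 5 days from Day 1; Section 4.3 allows up to 2 weeks. Section 2.5.1 lists "Late toxicities of GI ulceration or obstruction, esophageal stricture, pneumonitis, renal toxicity, liver toxicity, bone weakening". A secondary objective in the Section 1.1 synopsis is "To evaluate the safety and tolerability of radiotherapy added to olaparib".

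**Follow-up contacts.** In Section 1.3, AE review stops at the 30-day safety visit. The 12-weekly follow-up column carries survival status and imaging only. After progression or new therapy, patients "should be contacted by telephone every 12 weeks to assess for survival status until death". The one radiation-specific contact after SBRT is a nurse call at 2 weeks.

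**The concern.** The safety clock is tied to the wrong event for part of the regimen. Drug may continue for months or stop after one cycle, but SBRT is finished within the first two weeks for everyone. How long a patient is watched for radiation effects therefore depends on how long they take drug, which is unrelated to when a late radiation effect would appear.

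The gap falls mainly on patients who stop early. Non-serious strictures, ulcers or pneumonitis arising after their 30-day window would not be recorded. Serious ones may be recorded for a further 60 days but are then left out of the summaries. Both omissions can only lower the late-toxicity count reported for the combination.

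The collection part cannot be repaired at analysis, because non-serious events that were never recorded cannot be recovered. The primary ORR endpoint is unaffected.

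**Working it through.** The plan gives no figure on this point to reproduce. The check is calendar arithmetic plus a comparison of the sections.

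**Inputs**
- Last SBRT fraction, F: Day 5 (Section 6.1.2 table) to Day 14 (latest completion, Section 4.3).
- General AE window: last dose + 30 days (Section 8.3.1).
- SAE window: last dose + 90 days, if no new anticancer therapy starts (Section 8.3.2).
- First restaging: 9 weeks, Day 63 (Section 8.1.2.6.1), taken as a plausible early stopping point. Days 21 and 189 are added for comparison.

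**Days of radiation follow-up.** With last drug dose on day L, general AE coverage after SBRT is L + 30 − F and SAE coverage is L + 90 − F. For L = 63:
- General AEs: 63 + 30 = 93; 93 − 14 = 79 and 93 − 5 = 88 days.
- SAEs: 63 + 90 = 153; 153 − 14 = 139 and 153 − 5 = 148 days.

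| Last drug dose | General AE collection closes | Days after last fraction | SAE collection closes | Days after last fraction |
|---|---|---|---|---|
| Day 21 | Day 51 | 37 to 46 | Day 111 | 97 to 106 |
| Day 63 | Day 93 | 79 to 88 | Day 153 | 139 to 148 |
| Day 189 | Day 219 | 205 to 214 | Day 279 | 265 to 274 |

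If new anticancer therapy starts within 30 days of the last dose, the SAE column falls to the general AE figures. The analysed window equals the general AE window in every row, for AEs and SAEs alike.

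**The same sum in reverse.** The documents give no onset times, so these are assumed. A non-serious event starting T days after the last fraction is collected only if drug continues to at least day T + F − 30:
- T = 60: Day 35 to 44.
- T = 90: Day 65 to 74.
- T = 180: Day 155 to 164.

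For an SAE at T = 180 without new therapy, drug must continue to day T + F − 90, that is Day 95 to 104.

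**Sections side by side**
- Section 8.1.2.1 says adverse experiences are graded and recorded throughout the study and in follow-up. Section 8.3.1 says they are not collected after 30 days. The Section 1.3 follow-up column has no AE review.
- The Section 8.3.1 sentence makes no exception for serious events. Sections 8.3.2, 8.1.4.3 and 8.3.6 do.
- SAEs with onset on days 31 to 90 after the last dose are collected under Section 8.3.2 and excluded under Section 9.4.5.

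**The case against.** The case for leaving the plan alone has real content.

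- **Serious events have wider cover.** Hospitalised ulceration, obstruction or pneumonitis would normally meet seriousness criteria and be collected to 90 days. Potential drug-induced liver injury is reportable over the same period (Section 8.3.6.1). Section 8.3.1 defines a Merck product to include one distributed by Merck, and Section 6.2.1 has Merck handling olaparib shipments, so a serious event attributed to SBRT plus olaparib is arguably reportable without limit. All deaths are summarised.
- **Section 8.1.2.1 points the other way** on recording in follow-up, and Section 8.3.4 has investigators ask about AEs and SAEs at each study visit.
- **The endpoint is treatment-emergent events.** No endpoint promises a late-toxicity rate, and Section 2.5.1 gives no onset times.
- **Late reports would be weak data.** After progression, contact is by telephone. Many listed toxicities cannot be reliably graded or localised that way, and tumour growth or later therapy confounds them.

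A reader might infer that the listed toxicities go wholly unrecorded in early stoppers. The first bullet rules that out. A reader might also infer that changing the analysis window would be useless. That is wrong for SAEs with onset on days 31 to 90, which are already collected.

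What the objection does not remove: non-serious late events fall outside the explicit rule; the unlimited SAE route runs to Merck, is not stated to feed the trial dataset, and does not clearly cover an event attributed to SBRT alone; and Section 8.1.2.1 creates a contradiction for sites rather than a working collection procedure. The data-quality point limits the remedy but does not justify collecting nothing.

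**Conclusion.** The point holds in a bounded form. Late SBRT toxicity is incompletely captured in patients who stop drug early, and anything with onset more than 30 days after the last dose, apart from deaths, is not analysed. For a last dose on Day 63, radiation follow-up ends at 79 to 88 days for general AEs and at most 139 to 148 days for SAEs. Patients who stay on drug for many months are largely covered.

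The day counts rest only on the stated windows and on SBRT ending between Day 5 and Day 14. They describe observation time, not missed events. It is tempting to assume a distribution of time on drug and quote the share of patients outside the window at some landmark. The documents give no time on drug, onset time or incidence, and such a share would include patients who have died and cannot have an event. The direction of the error is clear: the late-toxicity count can only be too low. Its size cannot be estimated from the documents.

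The change is worth making because a stated secondary safety objective is affected and part of the loss is irreversible.

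**What to change.** 1. **Reconcile the windows.** Align Sections 8.1.2.1, 8.3.1, 8.3.2 and 9.4.5, together with the repeated SAE wording in 8.1.4.3 and 8.3.6, so that sites have one collection rule for non-serious events and one for SAEs. In Section 9.4.5, summarise all SAEs collected through the 90-day window. This uses data already gathered and costs only text and programming.

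2. **Add an SBRT-anchored rule to Section 8.3.1.** At the existing 12-weekly follow-up contacts, the site records any newly reported or diagnosed event on the Section 2.5.1 late-toxicity list considered possibly related to SBRT, whatever the time since the last drug dose. Record the CTCAE grade where available, and flag onset after progression or new anticancer therapy. Report these events descriptively, with follow-up time from the last SBRT fraction. Add the item to the Section 1.3 follow-up column, and adjust the Section 6.4.1 statement that patients on new therapy are followed for survival only.

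No new visit or procedure is needed. The cost is modest site time at those contacts and one more table. Telephone-reported events will be incompletely graded and confounded by progression or later treatment; the report should state this as a limitation and should not present the counts as a complete late-toxicity rate.
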